10.4.1. Guideline-appropriate screening

Guideline-appropriate screening in Australia is determined based on a clinicians' judgement of a patient's risk of CRC and recommendations in the 2017 Guidelines (3). In this study, patients aged 50-74 years will be classified as either guideline-appropriate screeners (those who undergo screening appropriate for their risk level as directed by their GP) or non-guideline-appropriate screeners (encompassing both under-screeners and over-screeners). For a detailed description of the criteria for guideline-appropriate, under- and over- screening (see Table 4). Contingency tables will be generated to represent the proportion of guideline-appropriate screeners and non-guideline-appropriate screeners in each trial arm, risk category, age group and sex.

For the primary clinical effectiveness outcome (*number of guideline-appropriate CRC screening tests completed by patients*), an incremental approach will be used to test the effect of the intervention. The first model (unadjusted model) will use the trial group as the sole fixed predictor. The second model (adjusted model) will add guideline risk category, gender, age, and socioeconomic status of the practice (based on SEIFA (34)) to the unadjusted model. The final model (effect modification model) will look at the interaction between treatment group and risk category to test whether the effect of the intervention was modified by risk category.

If the final model demonstrates significant effect modification, simple post hoc analyses will be performed at each risk level. Comparisons involving categorical predictors with more than two levels

will be corrected using the Westfall method, a step-down form of error correction that offers similar protection against type I error as traditional single-step methods such as the Bonferroni procedure but is less conservative and, therefore, less likely to overinflate p values and conceal genuine effects (35).

Table 4 Guideline-appropriate screening categorisation (3)

Risk category	Not guideline-appropriate/under screening	Guideline-appropriate screening	Not guideline-appropriate
At or slightly above average risk No FDR or SDR with colorectal cancer One FDR with colorectal cancer diagnosed at 55 years or older One FDR or SDR with colorectal cancer diagnosed at 55 years or older	No iFOBT in previous 2 years if 50 -74 years of age	One iFOBT every 2 years. if 50 -74 years of age as part of the NBCSP	More than one iFOBT in previous 2, OR Any colonoscopy
Moderately increased risk One FDR with colorectal cancer diagnosed under 55 years Two FDR with colorectal cancer diagnosed at any age One FDR and at least two SDR with colorectal cancer diagnosed at any age	No colonoscopy in previous 5 years	One colonoscopy every 5 years. CT colonography may be offered if colonoscopy is contraindicated	More than one colonoscopy in previous 5 years, OR iFOBT if colonoscopy has already been performed
Potentially high risk At least three FDR or SDR with colorectal cancer, with at least one diagnosed under 55 years At least three FDR with colorectal cancer diagnosed at any age	No colonoscopy in previous 5 years	One colonoscopy every 5 years. CT colonography may be offered if colonoscopy is contraindicated	More than one colonoscopy in previous 5 years
FDR = first-degree relative; iFOBT= immunochemical faecal occult blood test; SDR = second-degree relative			

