6.1. Background and rationale

Colorectal cancer (CRC) is the fourth most common cancer in Australia and screening for precancerous lesions and early stage cancer is proven to decrease CRC mortality and morbidity (1,2). In Australia, the National Bowel Cancer Screening Program (NBCSP) provides a self-administered stool test, the immunochemical faecal occult blood test (iFOBT), mailed to the home of all Australians aged 50-74 years. If an individual has above average risk of CRC (e.g., a family history of the disease), specialised screening regimens via colonoscopy are recommended in place of NBCSP screening (3). Optimising the NBCSP and ensuring people at above average risk are screening appropriately are critical to reducing CRC mortality and morbidity in Australia. The NBCSP alone has the potential to save 84,000 lives by 2040 if participation can reach and be sustained at 60% (4).

The CRC burden in Australia remains high and there are many people who do not screening according to the evidence-based guideline recommendations (3). That is, they either do not screen at all (under-screened) or screen using colonoscopy when they are not at above average risk (inappropriately screened). Under-screened individuals are at higher risk of developing advanced-stage CRC, whereas inappropriately screened individuals can place unnecessary strain on the healthcare system through low-value colonoscopies (5). Improving guideline-appropriate CRC screening will improve CRC outcomes and optimise the use of CRC-specific health services.

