8.1. Primary Outcomes

The trial will evaluate the primary outcomes of implementation and clinical effectiveness of the intervention by general practice.

- A. The co-primary **implementation effectiveness outcome** is guideline-appropriate CRC screening recommendations provided.
- B. The co-primary **clinical effectiveness outcome** is guideline-appropriate CRC screening tests completed by patients.

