10.3.1. Primary Outcomes

➤ Implementation effectiveness outcome

For the implementation effectiveness primary outcome (*number of guideline-appropriate CRC screening recommendations provided*), a study specific data collection instrument will be used and integrated into Clinical Information Systems (CIS) used in general practice. CISs are used by general practices to facilitate care at an individual patient level. Medical records are stored within the CIS and used by GPs to store information during consultations, such as patient bowel cancer screening history. The National Cancer Screening Register (NCSR) integrates with CIS to allow health providers access to patients' NBCSP participation history from within their CIS.

Medical Director is a CIS used widely across Australia and is already integrated into practices across NSW and WA. Medical Director will enter into an agreement with the University of Sydney under a "Education Support – Master Services Agreement". The agreement will include the development of an electronic prompt which will act as a study specific data collection instrument. Medical Director obtains consent from general practices where their software has been installed to participate in research project. Data will be extracted from the general practice CIS via Medical Director and is de-identified, and no identifiable data leaves the CIS. Medical Director data are managed in accordance with relevant privacy and health records legislation.

➤ *Clinical effectiveness outcome*

For the clinical effectiveness primary outcome of the *number of guideline-appropriate CRC screening tests completed by patients*, de-identified, aggregate patient data will be extracted from CIS. These data will be obtained from the PHN (Health Analytics Software).

PHNs collect data from general practice electronic medical records stored within their CIS through Health Analytics Software tools. The tools used render the data drawn from practice databases unidentifiable, enabling it to be disclosed for research purposes under the Privacy Act 1988 (Privacy Act). PHNs facilitate the licensing of Health Analytics Software to support the extraction, analysis and management of general practice data in the form of population health reports, including bowel cancer screening participation.

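### Table 4 counts any colonoscopy in an average-risk patient as not guideline-appropriate; this is broader than section 6.1 and overlaps the cell for correct iFOBT screening, with no rule for which prevails.

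*Protocol*

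**What the plan says.** Section 8.1 of the protocol gives the clinical co-primary as "guideline-appropriate CRC screening tests completed by patients". Section 10.4.1 makes the classification binary and per patient: "patients aged 50-74 years will be classified as either guideline-appropriate screeners" or as "non-guideline-appropriate screeners (encompassing both under-screeners and over-screeners"). It then makes Table 4 the operative definition: "For a detailed description of the criteria for guideline-appropriate, under- and over- screening (see Table 4").

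In the row for people at or slightly above average risk, the appropriate cell reads "One iFOBT every 2 years. if 50 -74 years of age as part of the NBCSP" and the last, not-appropriate cell reads "More than one iFOBT in previous 2, OR Any colonoscopy".

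Section 6.1 describes the over-screening problem as people who "screen using colonoscopy when they are not at above average risk (inappropriately screened").

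For the clinical co-primary, section 10.3.1 states that "de-identified, aggregate patient data will be extracted from CIS". The protocol describes no field for the reason for a colonoscopy or for the iFOBT result, and nowhere mentions colonoscopy after a positive iFOBT.

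**The concern.** Section 6.1 is about the test chosen for screening. Table 4 is about whether a colonoscopy has occurred at all. A patient who screens by iFOBT and then has a colonoscopy because of the result has not screened by colonoscopy, yet falls under the wording of the table. So does a patient whose colonoscopy was for symptoms or was done many years ago.

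Two things are at stake. First, the same patient fits two cells with opposite meanings, so two analysts, or two extraction tools, could code that patient differently. Second, under the literal reading some correct screeners are recorded as failures, and the measured absolute gain is smaller than the true one. Section 10.4 requires an absolute effect to be reported, and section 15 feeds the results into effectiveness and cost-effectiveness modelling. Because the data arrive as aggregate reports, a coding choice made at extraction may not be reversible afterwards.

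**Working it through.** **The wording, side by side (average-risk row)**

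| Patient aged 50-74 | Meets the appropriate cell? | Meets the not-appropriate cell? |
|---|---|---|
| One programme iFOBT in 2 years, no colonoscopy ever | Yes | No |
| One programme iFOBT, then follow-up colonoscopy | Yes | Yes |
| One programme iFOBT, colonoscopy many years ago | Yes | Yes |
| Colonoscopy used as the screening test, no iFOBT | No | Yes |

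Only the last patient matches the description in section 6.1. The second and third are the overlap, and no precedence rule resolves it. By contrast, the colonoscopy counts in the two higher-risk rows all carry a 5-year window.

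**Size**

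There is no figure in the plan to reproduce: the sample size in section 10.1.2 comes from a pilot rule of thumb and does not use this outcome's rate. The inputs below are assumptions for illustration.

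- iFOBT positivity: 4-10%.
- Colonoscopy among those positive: 60-90%.
- True proportions appropriate: 40% control, 45% intervention (difference 5.0 points, ratio 1.125, odds ratio 1.227).

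Share of correct iFOBT completers recoded under the literal reading, q = positivity × follow-up:

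- Low: 0.04 × 0.60 = 0.024.
- High: 0.10 × 0.90 = 0.090.

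Observed proportion = p × (1 − q).

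*Follow-up equal in both arms*

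- q = 0.024: 0.40 × 0.976 = 39.04%; 0.45 × 0.976 = 43.92%; difference 4.88 points.
- q = 0.090: 0.40 × 0.910 = 36.40%; 0.45 × 0.910 = 40.95%; difference 4.55 points.
- The ratio is 1.125 in both cases, since (1 − q) cancels. The odds ratio falls from 1.227 to 1.223 and 1.212 respectively.

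*Follow-up differing by arm (60% control, 90% intervention)*

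- Positivity 4%: 0.40 × 0.976 = 39.04%; 0.45 × 0.964 = 43.38%; difference 4.34 points, ratio 1.111.
- Positivity 10%: 0.40 × 0.940 = 37.60%; 0.45 × 0.910 = 40.95%; difference 3.35 points, ratio 1.089.

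*Past colonoscopy.* If a share c of patients has had a colonoscopy at any time, equally in both arms and unrelated to response, the absolute difference is multiplied by (1 − c) and the ratio is unchanged. The documents give no value for c, so no figure is put on this part.

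If colonoscopy after a qualifying iFOBT is exempted, the first two calculations return to 5.0 points and 1.125.

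**The case against.** **Failure coding is not stated.** A reader might infer that the protocol definitely counts these patients as failures. It does not say so. They also meet the appropriate cell, and the table's subject is screening, so the entry could be read as any screening colonoscopy. This stands: failure is the literal consequence of the word used, not an explicit rule. It does not remove the defect, because a table offered as the detailed criteria should not need that inference.

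**The co-primary is worded as a number of tests.** In a pure count of tests, with the Poisson or negative binomial model named in section 10.4, a later colonoscopy need not cancel a completed iFOBT. This also stands, and it limits the point to analyses that use the patient-level classification. Those are not remote: section 10.4 also plans a difference in proportions, and 10.4.1 defines appropriateness per patient. The protocol leaves the unit unclear.

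**Bias against the intervention.** A reader might infer that each additional test works against the intervention. It does not. An under-screened patient is already a failure, so a positive test followed by colonoscopy leaves the code unchanged. On the assumed inputs each extra completed iFOBT still adds 1 − 0.09 = 0.91 to 1 − 0.024 = 0.976 successes. The effect is attenuation, and the rate ratio is untouched when follow-up is equal by arm.

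**Section 10.3, Table 3 gives 12-month tracking.** This might be taken to exclude old colonoscopies. It does not settle the matter, since Table 4 itself needs 2-year and 5-year histories.

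**Look-back and precedence are analysis-plan detail.** Often they are. Here the protocol has fixed a rule, and that rule is broader than its own rationale. The missing unit after the number 2 is minor, since the first cell of the same row says years.

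**Conclusion.** The point holds as a defect in the outcome definition that should be corrected. The average-risk cell is wider than the concept in section 6.1 and overlaps the appropriate cell with no precedence. Taken literally, it misclassifies some correct screeners.

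On assumed positivity of 4-10% and follow-up of 60-90%, about 2-9% of completed tests would be recoded. A true 5.0-point difference (40% versus 45%, also assumed) would show as 4.9 to 4.6 points with the ratio unchanged. If follow-up were 60% in control and 90% in intervention, it would show as 4.3 to 3.4 points, with the ratio falling from 1.125 to 1.11-1.09. Nothing in the documents says that follow-up differs by arm.

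A reader might infer a much larger loss from patients with a past colonoscopy. The mechanism is real under the literal wording. Its size depends on how common past colonoscopy is, on whether the extract captures it, and on whether those patients respond as others do. The documents give none of these, so no large effect can be claimed.

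**What to change.** For outcome coding only, with no implication for care:

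1. Reconcile the average-risk row of Table 4 with section 6.1.
2. Add a precedence rule: a patient with one qualifying iFOBT in the window is coded guideline-appropriate even if a colonoscopy follows that iFOBT.
3. Otherwise, count colonoscopy as over-screening only within a stated look-back window, excluding those with a recorded diagnostic reason where the extract holds that field.
4. State whether the clinical co-primary counts tests or patients, and supply the missing time unit in the iFOBT part of the cell.
5. Put the rule in the dictionary of metrics foreseen in section 11.1.2 before the aggregate reports are drawn.
6. Report the present any-colonoscopy coding as a sensitivity analysis; both versions must be requested at extraction.

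Cost: a table footnote and dictionary entries, plus work on the extraction tools. They must order iFOBT and colonoscopy dates within a patient before aggregating, and eligible practices may use any of three products (Pen CS, Polar, Primary Sense), so feasibility should be confirmed for each. Downside: some screening colonoscopies after a negative iFOBT would no longer count as over-screening. The sensitivity analysis would show how far the result depends on the coding.

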10.5. Allocation and blinding process

Randomisation for this study will be carried out at the level of general practice. Each practice will be allocated to the intervention or usual care arm using a random computer-generated sequence by the Daffodil Centre research team. To account for differences in region-specific NBCSP screening rates, the randomisation will be stratified by participating states (NSW and WA). In each state, the same number of practices will be allocated to the intervention and usual care arms. Accordingly, GPs, general practice staff and their patients will be assigned to the intervention or usual care arm based on the assignment of their general practice.

10.7. Breaking the blind

Allocation of the trial groups will only be revealed to the statistician and investigators after all the primary and secondary outcome data have been collected and the results presented to the investigators.

10.8. Schedule of events

Table 5 Pilot trial schedule of events

TIME POINT**	STUDY PERIOD								
	Enrolment		Allocation	Post-allocation					Close-out
	Aug 2023	Sep 2023	Nov 2023	Jan 2024	March 2024	May 2024	July 2024	Sep 2024	Oct 2024
Visit window	+/- 30 days	+60 days	+/- 14 days	+/- 60 days	+/- 14 days	+/- 14 days	+/- 14 days	+/- 30 days	+/- 30 days
PHN Research Agreement	X								
Recruitment of CTCs	X								
ENROLMENT:									
Eligibility screen		X							
Informed consent		X							
Randomisation / Allocation			X						
INTERVENTIONS:									
Preparation of intervention			X	X					
Delivery of intervention					X				
Ongoing support from CTC (Intervention arm)					X	X	X	X	
Monitoring from CTC (Control arm)					X	X	X	X	
ASSESSMENTS:									
Baseline data collection		X	X						
clinical audit (primary outcome)		X	X	X					
Baseline surveys (secondary outcome)				X	X	X	X	X	
Ongoing data collection (secondary outcomes)									
Post-intervention data collection clinical audit (primary outcome)									X
Post-intervention surveys (secondary outcome)									X

Note: Pilot trial schedule of events: Study specific adapted from The University of Sydney Clinical Trials Study Protocol template.

10.9. Ethics approval

Ethics approval will be obtained from the University of Sydney Human Research Ethics Committee (HREC) before trial activities are commenced. Site-specific governance will be sought from the relevant PHN Research Governance Organisation (RGO) upon receiving notification of the approval.

10.10. General practice reimbursement

The Research Agreement will set out the trial timeline and expectations of participating practices, as well as how and when the practices will be paid (in two instalments, AUD\$1,000 6 months after trial commencement at the point of intervention delivery and \$AUD 1,000 upon completion of the trial, \$2,000 in total). The costing is in line with appropriate costing for research based in primary care outlined by PC4 'A guide to understanding budgets for primary care practice-based research'.

10.11. Monitoring of clinical trial

The Daffodil Centre, a joint venture between Cancer Council NSW and the University of Sydney research team, will monitor this trial. All members of the Daffodil Centre research team will complete Good Clinical Practice training.

The Coordinating Principal Investigator will send monitoring communication, including site visit confirmation emails, agendas, follow-up emails, etc, to the study sponsor and the University of Sydney Clinical Trials Risk and Governance team.

10.12. Continuation of therapy

The trial intervention activities, resources and support will be provided only within the 12-month trial period. The results will ascertain the effectiveness of the intervention and will contribute to the broader MAIL, GP & SCALE project, including a Scale-Up Plan.

Jurisdictional representatives of local health organisations that support the delivery of health programs have contributed to the design of the intervention. They will participate in activities to inform sustainability and scalability.

Resources used within the intervention, such as cancer screening toolkits, educational guides, and reminder prompts are existing and available to General Practice to access and utilise. Upon trial completion these resources will be made available through participating PHN websites and The Daffodil Centre website [The Daffodil Centre - The Daffodil Centre](#). Access links to resources will be disseminated to participating practices via a study-specific newsletter and through bowel screening outlets via the Research Team.

11. Data Management

11.1. Data storage and transfer of data to the Daffodil Centre

11.1.1. Data storage

All study data will be stored on the University of Sydney Research Data Store (RDS) and REDCap during the project and at completion. A project page will be established in the RDS and REDCap. The RDS is a secure, enterprise-grade Network Attached Storage device located within NSW. Study materials will be stored on the RDS during the project.

11.1.2. Process at General Practice Sites

The CTC (i.e., the persons named on the Site-Specific Assessment form) will be appointed as the trial REDCap and RDS Coordinators. The CTCs will oversee data collection, transfer and storage processes for each general practice site assigned to their coordination, n = 25 practices per CTC.

Table 6 summarises the General Practice data sets and storage.

Table 6 Description of General Practice data sets

Dataset	Contains identifiers	Data Custodian	Trial Storage location	Access provided to The Daffodil Centre
National Bowel Cancer Program Screening Data	✓	National Cancer Screening Register	General Practice	X
Clinical Information	✓	General Practice	General Practice	X

Systems software – medical records				
Health Analytics Software – POLAR, PenCS, Primary Sense Aggregate bowel cancer screening reports.	X	Primary Health Network	Research Data Store	✓

➤ *General Practice data*

The CTCs will work with the General Practice sites to coordinate data extraction within Clinical Information Systems by providing a dictionary of required metrics and practice support. The PHN receives the extracted de-identified data from the General Practice, facilitated through an established data-sharing agreement and Health Analytics Software. Once the de-identified practice data is uploaded to PHN, the PHN owns all rights and interests in and to the de-identified data. The PHN may use the de-identified data for any purposes that contribute to population health care.

[figure not shown]
The CTCs will coordinate the upload of extracted data in the form of de-identified aggregated reports from the PHN to the RDS. All data is de-identified - no identifiers (patient name, patient date of birth) will be extracted or included in the data reports. This mechanism means that the patient record data will not leave the General Practice sites. The CTC will not be involved in the de-identification of the patient datasets as the PHN data extraction tools have the required functionality ([see section 10.3](#)).

PHN Data Governance Officers will be contacted for advice on organizational procedures for collecting, storing, and transferring de-identified aggregate data reports. The outlined process of data transfer to the RDS will be provided to the PHN Data Governance Officers for advice and modification.

➤ *Transfer of general practice data to The Daffodil Centre (at CCNSW)*

The de-identified General Practice dataset will be securely transferred in the form of de-identified aggregate reports by the CTCs directly to the RDS. In the event the CTCs are unable to be established as external collaborators on the RDS project, the reports will be shared with the Daffodil Centre (at CCNSW) project team using a protected SharePoint Site administered by the Daffodil Centre, unless another transfer method is advised by the Data Governance Officers of the PHNs such as encrypted files with an encryption key shared separately to the data. CTCs using SharePoint Sites will only be able to access the Site for their designated General Practices. The Daffodil Centre (at CCNSW) project team will upload the de-identified data report to the RDS after the transfer is complete. The data stored on the RDS will be accessible only by the approved Daffodil Centre project team. Figure 2 below summarises the transfer of general practice data to the Daffodil Centre (at CCNSW) project team.

Figure 2 Transfer of General Practice data sets

[figure not shown]
➤ *General practitioner and practice staff data*

Independent REDCap projects will be created for each participating GP or practice staff member. GP and practice staff consent for study involvement will be obtained in REDCap. Once a General Practice has signed a Research Agreement to participate, the CTC will provide the staff members within the General Practice with a link to the REDCap study landing page that includes The Participant Consent form. After individual consent is obtained in REDCap, the CTC will flag identifiable information in REDCap and assign each participant a study-specific project person number (PPN) to create a de-identified dataset within REDCap. The CTC will manage the REDCap projects for their General Practice sites. The CTC will support the collection of data within REDCap at the site during the trial. As data is entered into REDCap for trial monitoring and process evaluation purposes, the CTC will flag the identifiable information, de-identify the data and link the data in REDCap to the PPN.

De-identified data will be retrieved from REDCap by the CTC and stored within the RDS. The REDCap project will be designed to enable data transfer throughout the study to the RDS, for the monitoring of implementation outcomes. The approved Daffodil Centre project team will have access to the RDS data sets. Access to the REDCap project will be restricted only to the CTCs. CTCs will be unable to access data and study files for other general practice sites enrolled in the study.

Figure 3 is provided at the end of this section summarising the transfer of datasets for the sub-study process evaluation described above.

Figure 3 Transfer of GP, practice staff data

